10.3.4 Reporting of SAEs

SAE reporting to the sponsor via an electronic data collection tool

- The primary mechanism for reporting an SAE to the sponsor will be the electronic data collection tool.
- If the electronic system is unavailable, then the site will use the paper SAE data collection tool (see next section) in order to report the event within 24 hours.
- The site will enter the SAE data into the electronic system as soon as it becomes available.
- After the study is completed at a given site, the electronic data collection tool will be taken off-line to prevent the entry of new data or changes to existing data.
- If a site receives a report of a new SAE from a study participant or receives updated data on a previously reported SAE after the electronic data collection tool has been taken off-line, then the site can report this information on a paper SAE form (see next section) or to the sponsor by telephone.

SAE reporting to via paper CRF (if the electronic system is unavailable)

- Facsimile transmission of the SAE paper CRF is the preferred method to transmit this information to the sponsor.
- In rare circumstances and in the absence of facsimile equipment, notification by telephone is acceptable with a copy of the SAE data collection tool sent by overnight mail or courier service.
- Initial notification via telephone does not replace the need for the Investigator to complete and sign the SAE CRF pages within the designated reporting time frames.

10.4 APPENDIX 4: CONTRACEPTIVE GUIDANCE AND COLLECTION OF PREGNANCY INFORMATION

10.4.1 Definitions

Woman of childbearing potential (WOCBP)

A woman is considered fertile following menarche and until becoming postmenopausal unless permanently sterile (see below).

If fertility is unclear (eg, amenorrhea in adolescents or athletes) and a menstrual cycle cannot be confirmed before first dose of study intervention, additional evaluation should be considered.

Women in the following categories are not considered WOCBP

1. Premenarchal
2. Premenopausal female with 1 of the following:
 - Documented hysterectomy
 - Documented bilateral salpingectomy
 - Documented bilateral oophorectomy

For individuals with permanent infertility due to an alternate medical cause other than the above, (eg, mullerian agenesis, androgen insensitivity), Investigator discretion should be applied to determining study entry.

Note: Documentation can come from the site personnel's: review of the participant's medical records, medical examination, or medical history interview.

3. Postmenopausal female
 - A postmenopausal state is defined as no menses for 12 months without an alternative medical cause.
 - A high FSH level in the postmenopausal range may be used to confirm a postmenopausal state in women not using hormonal contraception or hormonal replacement therapy (HRT). However, in the absence of 12 months of amenorrhea, confirmation with >1 FSH measurement (>40 IU/L or mIU/mL) is required.
 - Females on HRT and whose menopausal status is in doubt will be required to use one of the non-estrogen hormonal highly effective contraception methods if they wish to continue their HRT during the study. Otherwise, they must discontinue HRT to allow confirmation of postmenopausal status before study enrolment.

10.4.2 Contraception guidance

Recommended contraceptive methods are listed below in [Table 6](#).

Table 6 - Highly effective contraceptive methods

Highly effective contraceptive methods that are user dependent^a

Failure rate of <1% per year when used consistently and correctly

- Combined (estrogen- and progestogen-containing) hormonal contraception associated with inhibition of ovulation
 - oral
 - intravaginal
 - transdermal
- Progestogen-only hormone contraception associated with inhibition of ovulation
 - oral
 - injectable

Highly effective methods that are user independent

- Implantable progestogen-only hormonal contraception associated with inhibition of ovulation
 - Intrauterine device (IUD)
 - Intrauterine hormone-releasing system (IUS)
- Bilateral tubal occlusion
- Vasectomized partner:
Vasectomized partner is a highly effective contraceptive method provided that the partner is the sole sexual partner of the woman of childbearing potential and the absence of sperm has been confirmed. If not and less than 1 year after vasectomy, additional highly effective method of contraception should be used. Spermatogenesis cycle is approximately 90 days.)
- Sexual abstinence
Sexual abstinence is considered a highly effective method only if defined as refraining from heterosexual intercourse during the entire period of risk associated with the study treatment. The reliability of sexual abstinence needs to be evaluated in relation to the duration of the study and the preferred and usual lifestyle of the participant.

NOTES:

a Typical use failure rates may differ from those when used consistently and correctly. Use should be consistent with local regulations regarding the use of contraceptive methods for participants participating in clinical studies.

10.4.3 Collection of pregnancy information

Male AD participants with partners who become pregnant

- The Investigator will attempt to collect pregnancy information on any male participant's female partner who becomes pregnant while the male participant is in this study. This applies only to male participants who receive dupilumab.
- After obtaining the necessary signed informed consent from the pregnant female partner directly, the Investigator will record pregnancy information on the appropriate form and submit it to the Sponsor within 24 hours of learning of the partner's pregnancy. The female partner will also be followed to determine the outcome of the pregnancy. Information on the status of the mother and child will be forwarded to the Sponsor. Generally, the follow-up will be no longer than 6 to 8 weeks following the estimated delivery date. Any termination of the pregnancy will be reported regardless of fetal status (presence or absence of anomalies) or indication for the procedure.

Female AD participants who become pregnant

- The Investigator will collect pregnancy information on any female participant who becomes pregnant while participating in this study. The initial information will be recorded on the appropriate form and submitted to the Sponsor within 24 hours of learning of a participant's pregnancy.
- The participant will be followed to determine the outcome of the pregnancy. The Investigator will collect follow-up information on the participant and the neonate and the information will be forwarded to the Sponsor. Generally, follow-up will not be required for longer than 6 to 8 weeks beyond the estimated delivery date. Any termination of pregnancy will be reported, regardless of fetal status (presence or absence of anomalies) or indication for the procedure.
- Any pregnancy complication or elective termination of a pregnancy for medical reasons will be reported as an AE or SAE.
- A spontaneous abortion (occurring at <22 weeks gestational age) or still birth (occurring at >22 weeks gestational age) is always considered to be an SAE and will be reported as such.
- Any post-study pregnancy related SAE considered reasonably related to the study intervention by the Investigator will be reported to the Sponsor as described in [Section 8.5.4](#). While the Investigator is not obligated to actively seek this information in former study participants, he or she may learn of an SAE through spontaneous reporting.
- Any female participant who becomes pregnant while participating in the study will discontinue study intervention

10.5 APPENDIX 5: GENETICS

Use/Analysis of DNA or RNA

- Genetic variation may impact a participant's response to study intervention, susceptibility to, and severity and progression of disease. Variable response to study intervention may be due to genetic determinants that impact drug absorption, distribution, metabolism, and excretion; mechanism of action of the drug; disease etiology; and/or molecular subtype of the disease being treated. Therefore, where local regulations and IRB/IEC allow, blood samples will be collected for DNA/RNA analysis from study participants consenting to participate in the research substudy ([Section 8.7](#)). Also, leftover skin biopsies or related material will be included in the research substudy.
- In addition to the planned RT-qPCR, ISH and N-DSP analyses of skin biopsy derived RNA described in [Section 8.7](#), biopsy and blood samples from participants consenting to future research and from which DNA/RNA could be extracted and analyzed will be used for research as described in [Section 8.7](#). The tissue and any isolated DNA/RNA thereof may also be used to develop tests/assays including diagnostic tests related to dupilumab and AD or related Type 2 immune diseases. Genetic research may consist of the analysis of one or more candidate genes or the analysis of genetic markers throughout the genome.

- DNA and RNA samples may be used for genetic, transcriptomic and/or expression analysis. This analysis may include standard targeted methods, such as qPCR genotyping, RT-qPCR, or microarrays, as well as DNA or RNA whole genome, exome or transcriptome sequencing. Additional analyses may be conducted if it is hypothesized that this may help further understand the clinical data.
- The samples may be analyzed as part of a multi-study assessment of genetic factors involved in the response to dupilumab or study interventions of this class to understand study disease or related conditions.
- The results of genetic analyses may be reported in the CSR or in a separate study summary.
- The Sponsor will store the DNA/RNA samples in a secure storage space with adequate measures to protect confidentiality.
- The samples will be retained while research on dupilumab or Type 2 immune diseases continues but no longer than 15 years or other period as per local requirements.

10.6 APPENDIX 6: COUNTRY-SPECIFIC REQUIREMENTS

Not applicable.

10.7 APPENDIX 7: ABBREVIATIONS

| | |
|-----------|---|
| AD: | atopic dermatitis |
| ADCT: | Atopic Dermatitis Control Tool |
| ADR: | adverse drug reaction |
| AE: | adverse event |
| AESI: | adverse event of special interest |
| BMI: | body mass index |
| CGRP: | calcitonin gene-related peptide |
| ClinRO: | clinician reported outcomes |
| COPD: | chronic obstructive pulmonary disease |
| COVID-19: | Coronavirus Disease 2019 |
| CRSwNP: | chronic rhinosinusitis with nasal polyposis |
| CSR: | clinical study report |
| DLQI: | Dermatology Life Quality Index |
| DTP: | Direct to Patient |
| EASI: | Eczema and severity index |
| eCRF: | electronic case report form |
| EoE: | eosinophilic esophagitis |
| EoS: | end of study |
| EoT: | end of treatment |
| EU: | European Union |
| GCP: | Good Clinical Practice |

| | |
|----------|--|
| HBcAb: | hepatitis B core antibody |
| HBsAg: | hepatitis B surface antigen |
| HBV: | hepatitis B virus |
| HCV: | hepatitis C virus |
| HCVAb: | hepatitis C virus antibody |
| HIV: | human immunodeficiency virus |
| IB: | Investigator's Brochure |
| ICF: | informed consent form |
| IGA: | Investigator Global Assessment |
| IgE: | immunoglobulin E |
| IHC: | immunohistochemistry |
| IL: | interleukin |
| IL-4Ra: | interleukin-4 receptor alpha |
| IMP: | investigational medicinal product |
| ISH: | in situ hybridization |
| ISR: | injection site reaction |
| ITT: | intent-to-treat |
| MedDRA: | Medical Dictionary for Regulatory Activities |
| NBF: | neutral buffered formalin |
| N-DSP: | Nanostring-Digital Spatial Profiling |
| NRS: | numeric rating scale |
| PACAP: | pituitary adenylate cyclase-activating polypeptide |
| PCSA: | potentially clinically significant abnormality |
| PFA: | paraformaldehyde |
| PGP9.5: | protein gene product 9.5 |
| PK: | pharmacokinetics |
| PN: | prurigo nodularis |
| POEM: | Patient Oriented Eczema Measure |
| PRO: | patient-reported outcome |
| PROMIS: | Patient-Reported Outcomes Measurement Information |
| PT: | preferred term |
| Q2W: | every 2 weeks |
| QoL: | quality of life |
| RT-qPCR: | reverse transcription quantitative polymerase chain reaction |
| SAE: | serious adverse event |
| SC: | Subcutaneous |
| SCORAD: | Scoring Atopic Dermatitis |
| SoA: | schedule of activity |
| SOC: | system organ class |
| TB: | tuberculosis |
| TCS: | topical corticosteroids |
| TEAE: | treatment-emergent adverse events |
| Th2: | T helper cell 2 |
| TSLP: | thymic stromal lymphopoietin |
| US: | United States |
| VIP: | vasoactive intestinal peptide |

10.8 APPENDIX 8: PROTOCOL AMENDMENT HISTORY

The Protocol Amendment Summary of Changes Table for the current amendment is located before the Table of Contents (TOC).

POEM:	patient oriented eczema measure
PROMIS:	Patient-Reported Outcomes Measurement Information
PT:	preferred term
Q2W:	every 2 weeks
QoL:	quality of life
SAP:	statistical analysis plan
SAS [®] :	Statistical Analysis System [®]
SC:	subcutaneous
SCORAD:	SCORing Atopic Dermatitis
SD:	standard deviation
SEM:	standard error of the mean
SOC:	system organ class
STD:	statistical technical document
TE:	treatment-emergent
TEAE:	treatment-emergent adverse event
VAS:	visual analogue scale
WHO-DD:	World Health Organization Drug Dictionary

1 STATISTICAL AND ANALYTICAL PROCEDURES

1.1 INTRODUCTION

The purpose of this document is to provide additional technical details.

A comprehensive and detailed description of strategy and statistical technique used to perform the analysis of data was provided in Section 9 of the protocol (Version 1 dated on 17AUG2020 and Amended version dated on 06JAN2021).

As specified in the protocol, the biomarker analyses will not be part of this document and a specific dedicated statistical analysis plan (SAP) will be produced in addition to this statistical technical document (STD).

Adverse events and medical history terms will be coded according to the Medical Dictionary for Regulatory Activities (MedDRA Version 25.0).

Previous and concomitant medication records will be coded according to the World Health Organization Drug Dictionary (WHO-DD version March 2022).

The reporting of the safety statistical analyses will be programmed according to the recommendations and templates of the BTD-009094 “Summarizing and reporting standard Early Development clinical trial data (except oncology)” Version 4.0 dated 02-Feb-2021. For vital signs parameters, the analyses of abnormalities will be based on the definitions of potentially clinically significant abnormalities (PCSAs) from BTD-009536 “Analysis and reporting of safety data from Clinical Trials through the Clinical Study Report” Version 3.0 dated 24-May-2014 (Appendix 3) and displayed in [Section 3.1](#).

1.2 MODIFICATIONS FROM THE STATISTICAL SECTION OF THE PROTOCOL

Following minor changes and clarifications were made to the statistical section of the protocol (amended version dated on 06JAN2021).

1.2.1 Observation period definition

For the AD participants, the overall observation period will be divided into 3 segments as follows:

- The pre-treatment period is defined as the period up to the first investigational medicinal product (IMP) administration.
- The treatment-emergent (TE) period is defined as the period from the IMP administration up to the end of treatment (EOT) visit (included).
- The post-treatment period (ie, the follow-up extension period) is defined as the period from the end of the TE period.

For the healthy participants, the overall observation period will be divided into 2 segments as follows:

- The screening period is defined as the period of 21 days up to the collection of the skin biopsy.
- The observational period is defined as the period of 7 days following collection of the skin biopsy.

1.2.2 Analysis visits

Except for the baselines, only observations from visits and/or timepoints planned in the protocol will be used in descriptive statistics. Usually, all timepoints planned in the protocol should be described.

All the data collected from eDiary (home dosing and patient-reported outcome) were linked to a unique unscheduled or a missing visit in the SDTM database. To perform the analysis by visit, the following visit window algorithm is defined.

VISIT WINDOW ALGORITHM		
Type of data	Planned visits in the protocol	Time interval for analysed visits
Home dosing		
Dupilumab administration	D29	23 to 36 days after the first IMP administration
	D57	51 to 64 days after the first IMP administration
	D71	65 to 78 days after the first IMP administration
	D85	79 to 92 days after the first IMP administration
	D99	93 to 106 days after the first IMP administration
Patient-Reported Outcomes		
Peak pruritus NRS	D1	Less than 28 days before the first IMP administration
	From D2 to D28	x days after the first IMP administration for each Dx
	D36	29 to 39 days after the first IMP administration
	D43	40 to 46 days after the first IMP administration
	D50	47 to 53 days after the first IMP administration
	D57	54 to 60 days after the first IMP administration
	D64	61 to 67 days after the first IMP administration
	D71	68 to 74 days after the first IMP administration
	D78	75 to 81 days after the first IMP administration
	D85	82 to 88 days after the first IMP administration
	D92	89 to 95 days after the first IMP administration
	D99	96 to 102 days after the first IMP administration

VISIT WINDOW ALGORITHM		
Type of data	Planned visits in the protocol	Time interval for analysed visits
	D106	103 to 109 days after the first IMP administration
	D113	110 to 116 days after the first IMP administration
	D120	117 to 123 days after the first IMP administration
	D127	124 to 130 days after the first IMP administration
	D134	131 to 137 days after the first IMP administration
	D141	138 to 197 days after the first IMP administration
Sleep quality NRS	D1	Less than 28 days before the first IMP administration
Skin pain NRS	D15	2 to 29 days after the first IMP administration
Skin Sensitivity NRS	D43	30 to 57 days after the first IMP administration
Skin Burning NRS	D71	58 to 85 days after the first IMP administration
	D99	86 to 106 days after the first IMP administration
	D113	107 to 127 days after the first IMP administration
	D141	128 to 197 days after the first IMP administration
POEM	D1	Less than 28 days before the first IMP administration
DLQI	D43	2 to 57 days after the first IMP administration
PROMIS-itch	D71	58 to 85 days after the first IMP administration
	D99	86 to 106 days after the first IMP administration
	D113	107 to 127 days after the first IMP administration
	D141	128 to 197 days after the first IMP administration

If more than one record occurs within the same visit window where only one assessment is expected, then the following rule will be applied: for D1, the last non-missing result prior to study drug administration will be used; for post-treatment assessments the closest non-missing result to the scheduled visit will be used. Then, for post-treatment assessments, if more than one record remain analyzable (ie, two records or more the same day), the first one will be used.

1.2.3 Participant demographic characteristics, medical history, and diagnoses

1.2.3.1 *Other baseline characteristics*

As there are not any other baseline characteristics, the planned listing will not be produced.

1.2.3.2 *Medical/surgical history*

Medical/surgical histories will be summarized by system organ class (SOC), high level term (HLT) and preferred term (PT), and listed.

1.2.4 Compliance

As the exact dose is not recorded in the database for the home dosing, the above-planned and under-planned dosing percentages will not be analyzed.

1.2.5 Prior/Concomitant medication/therapy

Concomitant medications will be summarized by anatomic category (first digit of the anatomic therapeutic class (ATC)) and therapeutic category (first three digits of the ATC). All ATC codes corresponding to a medication will be summarized, and participants will be counted once in each ATC category (anatomic or therapeutic) linked to the medication. Therefore, participants may be counted several times for the same medication.

A specific listing of rescue medications will also be performed. The rescue medications will be identified with “RESCUE THERAPY” as reason for treatment. The following information will be added in the listing: demographic data, dose regimen, reason for treatment...

1.2.6 Efficacy analyses

No imputation will be performed for the following efficacy analyses.

1.2.6.1 Primary endpoints

The two primary endpoints (intraepidermal nerve fiber density and branching by PGP9.5 antibody staining in lesional skin) was planned to be analyzed as quantitative endpoints. But the branching is a semi-quantitative endpoint with 4 modalities: “only linear”, “mainly linear”, “mainly branched” and “only branched” fibers. The statistical method will be updated as follows:

- The number and percentage of participants for each modality will be described by timepoints, by skin type (Lesional pruritic skin, Post-lesional healed skin non-pruritic non-lesional, Lesional non-pruritic skin and Non-lesional skin) and by treatment group based on the mITT and ITT population. Only the evaluable participants will be taken into account in the calculation of the percentages.
- The listing of individual data will be performed, including the following information: demographic data, location, laterality and directionality...
- No plots will be performed.

To analyze the change from baseline on Week 17 for intraepidermal nerve fiber density by PGP9.5 antibody staining in lesional skin, the summary plots for AD participants based on the mITT population (and on the ITT population) will be graphs of mean +/- standard error of the mean (SEM) for raw data, absolute and percent change from baseline at baseline (ie, 0) and Week 17.

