8.3.1 Skin biopsy samples

Skin biopsies of 4 mm diameter each will be collected from healthy participants and AD participants at time points according to the SoA ([Section 1.3](#)). Study staff will provide instructions regarding suture removal, if sutures are used for closure.

Gelfoam®, a hemostatic, can be applied for biopsy closure. Study staff will notify the patient this will dissolve and provide instructions regarding wound dressing and care.

The skin biopsy samples will serve to study the neuronal architecture (neuroanatomy) and neuromarkers in the epidermis of pruritic lesional skin before start of treatment with dupilumab and localisation matched post-lesional healing skin areas after EoT with dupilumab in AD participants. Accordingly, the collection of 4 biopsies in total is mandatory for AD participants at the following timepoints:

- Baseline: 2 biopsies of 4 mm diameter each at baseline before start of treatment from pruritic lesional skin.
- Week 17: 2 biopsies of 4 mm diameter each from non-pruritic, post-lesional healed or healing skin, with localisation matched to the baseline pruritic lesional biopsy.
 - if post-lesional healed skin that is completely non-pruritic non-lesional is not available at later visits, one of the following biopsies should be collected (in the order of relevance): 1. lesional non-pruritic skin, 2. Post-lesional pruritic skin or 3. lesional pruritic skin.

Participants who refrain from providing these biopsies at baseline and Week 17 are not eligible for this study.

Collection of the following additional biopsies is optional for AD patients, including

- 2 biopsies of 4 mm diameter each from non-pruritic, post-lesional healed or healing skin, localisation matched to the baseline pruritic lesional biopsy, at week 3 and at the end of the observation period at Week 21.
 - if post-lesional healed skin that is completely non-pruritic non-lesional is not available at later visits, one of the following biopsies should be collected (in the order of relevance): 1. lesional non-pruritic skin, 2. Post-lesional pruritic skin or 3. lesional pruritic skin.
- 2 biopsies of 4 mm diameter each from *non-lesional skin* at baseline.

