8.3.2 Neuroanatomy/Neuronal architecture

#A skin biopsy samples will be investigated for epidermal neuroanatomy/neuronal architecture. Briefly, the PFA-fixed part of the biopsies will be used to analyze the epidermal nerve fiber density and anatomy. Nerve fibers will be visualized by staining consecutive sections for the pan-axonal marker protein gene product 9.5 (PGP9.5); the basement membrane will be visualized by staining for collagen type 4 in order to determine exactly the point of invasion of nerve fibers into the epidermis.

Quantification of intraepidermal nerve fiber density will be calculated by assessing nerve fibers crossing the basement membrane per square millimetre (F/mm²).

Branching of epidermal nerve fibers will be assessed semi-quantitatively by classifying patients into 4 groups comprised of only linear, mainly linear, mainly branched or only branched fibers.

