1.2.6.2 Secondary endpoints

To analyze the changes from baseline on Weeks 3 and 21 for intraepidermal nerve fiber density and branching by PGP9.5 antibody staining in lesional skin, the summary plots for AD participants based on the mITT population (and on the ITT population, if applicable) will be graphs of mean +/- SEM for raw data, absolute and percent change from baseline at baseline (ie, 0), Week 3 and Week 21.

To analyze the changes from baseline on Weeks 3 and 21 for intraepidermal nerve fiber density and branching by PGP9.5 antibody staining in lesional skin and changes from baseline over time and at Weeks 17 and 21 for the outcomes of the assessments/questionnaires (peak pruritus assessed by numeric rating scale (NRS), eczema and severity index (EASI), scoring atopic dermatitis (SCORAD), patient-reported outcomes measurement information (PROMIS-itch), patient oriented eczema measure (POEM), dermatology life quality index (DLQI), atopic dermatitis control tool (ADCT) and sleep quality/skin pain/skin sensitivity/skin burning NRS), the individual profiles over time will be spaghetti plots on raw data with all the AD participants on the same graph and the AD group mean.

To analyze the changes from baseline over time and at Weeks 17 and 21 for the outcomes of the assessments/questionnaires, the following variables will be analyzed:

- Peak pruritus assessed by numeric rating scale (NRS): scale of the worst itch (from 0 ("no itch") to 10 ("Worst itch imaginable")).
- Eczema and severity index (EASI): composite index ranging from 0 to 72 calculated as follows. The intermediate and total EASI scores will be derived, however, only the total EASI score will be analyzed.
 - Severity scores: for each region (Head and neck, Trunk, Upper limbs and Lower limbs), the severity score will be derived as follows, ranging from 0 to 12:

$$\text{Severity score}_R = \text{Intensity score}_{\text{Erythema}, R} + \text{Intensity score}_{\text{Edema/Papulation}, R} + \text{Intensity score}_{\text{Excoriation}, R} + \text{Intensity score}_{\text{Lichenification}, R},$$

where R = region.

- Region scores: for each region, the region score will be derived as follows:

$$\text{Region score}_R = \text{Severity score}_R * \text{Area score}_R * \text{Multiplier}$$

where R = region, Multiplier = 0.1 for Head and Neck region, 0.3 for Trunk, 0.2 for Upper Limbs, 0.4 for Lower Limbs.

- Total EASI score will be derived as the sum of the 4 region scores.

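### The SAP plans no paired summary of Week 17 change for the second primary endpoint (nerve fiber branching), omits one permitted biopsy type, and averages this uncoded four-class variable at Weeks 3 and 21

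*SAP*

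**What the plan says.** Protocol Section 3 (Table 1) and Section 9.4.7 (Table 4) name two primary endpoints, both changes from baseline to Week 17 in lesional skin: intraepidermal nerve fiber density and nerve fiber branching. Protocol 8.3.2 defines how branching is measured: "Branching of epidermal nerve fibers will be assessed semi-quantitatively by classifying patients into 4 groups". The classes are only linear, mainly linear, mainly branched and only branched. No scores are attached to them.

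SAP 1.2.6.1 notes that the protocol had treated both endpoints as quantitative, and corrects this: "But the branching is a semi-quantitative endpoint with 4 modalities". Its replacement method is: "The number and percentage of participants for each modality will be described by timepoints, by skin type". The skin types are listed as "by skin type (Lesional pruritic skin, Post-lesional healed skin non-pruritic non-lesional, Lesional non-pruritic skin and Non-lesional skin". Percentages use evaluable participants only. A listing of individual data is added, and plots are ruled out.

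Protocol 8.3.1 asks for the Week 17 biopsy from healed or healing, non-pruritic post-lesional skin, matched in location to the baseline biopsy. If that is not available, it permits in order: "1. lesional non-pruritic skin, 2. Post-lesional pruritic skin or 3. lesional pruritic skin".

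For Weeks 3 and 21, SAP 1.2.6.2 names density and branching together and plans graphs of "mean +/- SEM for raw data, absolute and percent change from baseline at baseline (ie, 0), Week 3 and Week 21". It also plans "spaghetti plots on raw data with all the AD participants on the same graph and the AD group mean".

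**The concern.** There are three linked problems.

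1. The endpoint is a within-participant change, but the planned summary is a set of class counts at each timepoint. Such counts do not show who moved where. Density keeps its absolute and percent change in the same SAP section, so branching is the only primary endpoint that has lost its change analysis.
2. The split by skin type widens the gap. The baseline lesional biopsies are lesional pruritic, while most Week 17 biopsies should be post-lesional, so the two halves of a pair usually sit in different categories. A Week 17 biopsy of post-lesional pruritic skin has no category at all.
3. At Weeks 3 and 21 the SAP averages a variable that it has just called semi-quantitative. Without codes, the plotted level and percent change have no defined value.

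At stake is whether a primary endpoint is reported as defined. Error rates and sample size are not involved, because Protocol 9.1 predefines no hypothesis test.

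**Working it through.** **Step 1. The texts side by side.** The plan gives no figure to reproduce here.

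| Item | Protocol | SAP 1.2.6.1 |
|---|---|---|
| Quantity | Week 17 change in branching (Section 3; 9.4.7) | Class counts per timepoint |
| Scale | Four classes, no codes (8.3.2) | Four classes, no codes |
| AD skin types | Five: lesional pruritic; post-lesional healed or healing, non-pruritic; lesional non-pruritic; post-lesional pruritic; non-lesional (8.3.1) | Four: post-lesional pruritic is absent |
| Denominator | Not stated | Evaluable participants; no set with both biopsies is defined |

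**Step 2. What counts alone leave open at Week 17.** Protocol 9.2 gives about 34 AD participants and 20% drop-out: 34 x 0.8 = 27.2, taken as 27 pairs. The class counts below are assumed for illustration.

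| | Only linear | Mainly linear | Mainly branched | Only branched |
|---|---|---|---|---|
| Baseline | 3 | 6 | 12 | 6 |
| Week 17 | 6 | 12 | 6 | 3 |

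Let n_ij be the number in class i at baseline and class j at Week 17, with classes ordered from linear to branched. The published table fixes only the row and column sums. Less branched is L = sum of n_ij with j < i. More branched is M = sum with j > i. Unchanged is U = sum of n_ii. Minimizing and maximizing each over all whole-number tables with these sums gives:

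| Moves allowed | L | M | U | Net (L - M) |
|---|---|---|---|---|
| Any | 9 to 24 | 0 to 12 | 0 to 18 | 3 to 21 |
| At most two classes | 9 to 21 | 0 to 12 | 0 to 18 | 3 to 18 |
| At most one class | 15 to 21 | 0 to 6 | 0 to 12 | 15 |

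The unrestricted net shift runs from 3/27 = 11% to 21/27 = 78%. Three tables with the same sums (rows are baseline classes) show how this happens:

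- A: [3 0 0 0], [0 6 0 0], [3 3 6 0], [0 3 0 3]. L = 3+3+3 = 9, M = 0, U = 3+6+6+3 = 18.
- B: [0 3 0 0], [0 0 6 0], [6 3 0 3], [0 6 0 0]. L = 6+3+6 = 15, M = 3+6+3 = 12, U = 0.
- C: [0 0 0 3], [6 0 0 0], [0 12 0 0], [0 0 6 0]. L = 6+12+6 = 24, M = 3, U = 0.

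Tables A and B use moves of at most two classes, which is why U keeps its full range in the second row.

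**Step 3. Coding at Weeks 3 and 21.** No n is assumed, because Protocol 8.3.1 says: "Collection of the following additional biopsies is optional for AD patients". Percent change for one step toward linear is -1 divided by the baseline code:

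| Baseline class | Codes 0 to 3 | Codes 1 to 4 |
|---|---|---|
| Only branched | -1/3 = -33% | -1/4 = -25% |
| Mainly branched | -1/2 = -50% | -1/3 = -33% |
| Mainly linear | -1/1 = -100% | -1/2 = -50% |

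For a participant who starts at only linear, percent change divides by 0 with codes 0 to 3 and is undefined. Mean absolute change is the same under both codings, since (y + 1) - (x + 1) = y - x. Both codings assume equally spaced classes, which the documents do not state.

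**The case against.** - **The biomarker SAP may hold the table.** SAP 1.1 sends biomarker analyses to a separate document, and Protocol 9.2 counts neuronal architecture among the biomarker data. That document was not available, so the gap is shown only for this SAP. But 1.2.6.1 sets the branching method itself, and within 1.2.6 only the exploratory endpoints (1.2.6.3) are deferred.
- **Counts do show group change.** In the example the two branched classes fall from 18/27 to 9/27. The net movement is 15 class steps in every compatible table: with codes 0 to 3, the sum is 6 + 24 + 18 = 48 at baseline and 12 + 12 + 9 = 33 at Week 17. The widest ranges need large opposing moves. This is fair for complete pairs once skin types are pooled. The SAP defines no such set, and the number of participants who improved or worsened stays unknown.
- **Individual data are planned.** The listing, and possibly the profiles in 1.2.6.2, keep the pairing. With about 34 participants the change could be rebuilt by hand. That limits the harm, but a listing is not a summary.
- **The averaging may be carried-over wording.** SAP 1.2.6.1 rules out plots for branching, and SAP 1.3 gives frequencies for qualitative parameters. That may explain the text, but 1.2.6.2 names branching in both plot paragraphs, so the conflict has to be resolved.
- **The missing category may be empty.** SAP 1.2.2 shows that the database had been looked at, so the list may hold only observed types. The SAP does not say so.

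**Conclusion.** The concern holds and should be fixed. Followed as written, the SAP does not summarize the second primary endpoint as a change, leaves one permitted biopsy type without a category, and at Weeks 3 and 21 plots a percent change that depends on an unstated coding. These conclusions rest on the text alone.

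The ranges are illustrations. They depend on 27 pairs and on assumed class counts, and they narrow when large moves are ruled out. That counts at two timepoints do not determine paired change does not depend on those assumptions. The consequence is limited to reporting: the study is exploratory and descriptive, the data needed are collected, and whether the biomarker SAP fills the gap is unknown.

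**What to change.** In SAP 1.2.6.1, for AD participants:

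- Add a 4x4 shift table of the baseline lesional biopsy against the location-matched Week 17 biopsy, over participants with both classifiable. Report n (%) toward linear, unchanged and toward branched.
- A confidence interval for the net shift is optional. The protocol's level in Table 4 is 90%.
- Keep the table by skin type and add a category for post-lesional pruritic skin.
- If the biomarker SAP already holds the shift table, a cross-reference is enough.

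In SAP 1.2.6.2:

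- Give the same shift table for Weeks 3 and 21 on the pairs available.
- Remove branching from the mean and SEM plots and the percent-change plots, and drop its group mean.
- Individual ordinal profiles can stay: Protocol Table 4 plans them, and they keep the pairing.

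The cost is one extra table per visit and some SAP wording. No new data are needed.
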